15.4. Risks Associated with Participation in this Clinical Investigation

The risks involved with this study are comparable to those associated with the implant of any other commercially available neurostimulation system. Risks specific to Abbott neurostimulation systems are outlined in the associated IFU, and these disclosed risks are not modified by participation in this study.

15.5. Steps Taken to Control or Mitigate Risks

The Sponsor will employ measures throughout the course of this study to minimize these risks such as clearly defined inclusion and exclusion criteria, proper consenting process, selection of investigational sites that have a sufficient level of clinical expertise, investigator selection, and

Clinical Investigation Plan

appropriate training for all involved in the study activities. In-depth recommendations, special precautions and instructions regarding patient selection, device handling, device placement and system removal are included in IFU documents of all devices included in this study. All device-related adverse events and device deficiencies will be reported to the Sponsor and will be monitored internally for safety surveillance purposes.

15.6. Risk to Benefit Rationale

The risks associated with Abbott's neurostimulation systems are anticipated to be comparable to those associated with the use of other commercially available neurostimulation systems. The patients participating in this study are indicated for using a neurostimulation system as part of their standard medical management and are subject to the risks associated with these devices. Refer to the Investigational Brochure for details.

APPENDIX I: ABBREVIATIONS AND ACRONYMS

AE	Adverse Event
CEC	Clinical Events Committee
CIP	Clinical Investigation Plan
CP	Clinician Programmer
CRF	Case Report Form
DD	Device Deficiency
DMP	Data Management Plan
EC	Ethics Committee
EDC	Electronic Data Capture
FAS	Full Analysis Set
GCP	Good Clinical Practice
IB	Investigator Brochure
ICF	Informed Consent Form
IFU	Instructions for Use
IPG	Implantable Pulse Generator
MRI	Magnetic Resonance Imaging
NRS	Numerical Rating Scale
PRO	Patient Reported Outcome
PROMIS	Patient-Reported Outcomes Measurement Information System
SAE	Serious Adverse Event
SCS	Spinal Cord Stimulation
SD	Standard Deviation
UADE	Unanticipated Adverse Device Effect
USADE	Unanticipated Serious Adverse Device Effect

Clinical Investigation Plan

APPENDIX III: LABELS

IFU documents will be kept under a separate cover and are available upon request.

Clinical Investigation Plan

APPENDIX IV: CASE REPORT FORMS

Case Report Forms will be kept under a separate cover and are available upon request.

Clinical Investigation Plan

APPENDIX V: INFORMED CONSENT FORM

The study specific sample Informed Consent Form will be kept under a separate cover and is available upon request.

Clinical Investigation Plan

APPENDIX VI: MONITORING PLAN

A copy of the Monitoring Plan can be obtained upon request from the Sponsor Clinical Project Manager for the clinical investigation.

Clinical Investigation Plan

APPENDIX VII: EXPLANT, RETURN AND ANALYSIS OF THE IPG

The disposition of explanted Gemini SCS IPGs warrants special consideration, as their proper return will allow for analysis, providing valuable information on performance and possible failure modes.

Clinical study sites' responsibilities for explant and return of the device: Abbott requests that all Gemini SCS IPGs which are explanted by the investigators, or are explanted at other sites and recoverable by the investigators, be returned to Abbott as follows:

- Contact the Abbott clinical manager(s) for the study as soon as it is learned that the IPG will be (or has been) explanted. The clinical manager(s) will provide shipping instructions to ensure the IPG is delivered to Abbott Neuromodulation's Product Performance group for failure analysis. Note: Device(s) shall be shipped to the return address as soon as possible and no later than 15 calendar days.
- Used devices may present a health hazard. All possible safety measures shall be taken when handling used or explanted products to reduce the potential for staff to come into physical contact with potentially contaminated devices. Ensure that the device is free of gross contamination. If necessary, remove moisture by wiping with a dry cloth or towel. Note: Do not sterilize or sanitize the device.
- Place the device in a leakproof biohazard container or bag, and seal.
- Place the biohazard container or bag into a Device Return Kit. Include sufficient packing materials so that the biohazard container or bag is packed snugly. The outer packaging must be clearly labelled as "Biohazard".
- If the explant is associated with any alleged device deficiency, include a description of the deficiency. Clearly print the Return number and/or Product Event Record (PER) number on the outside of the sealed box.
- Follow all instructions of the Abbott clinical manager in shipping the explanted device to:

Attn: Abbott Returns Department
[name]
[name] USA

Abbott responsibilities for the analysis of an explanted and returned device: Gemini SCS IPGs that are explanted and returned will, upon receipt at Abbott, be evaluated according to Abbott's normal failure analysis practice for returned product.

Clinical Investigation Plan

APPENDIX VIII: REVISION HISTORY

Amendment Number	Version	Date	Details	Rationale
[REDACTED]	[REDACTED]	[REDACTED]	[REDACTED]	[REDACTED]
[REDACTED]	[REDACTED]	[REDACTED]	[REDACTED]	[REDACTED]

Clinical Investigation Plan

APPENDIX IX: CIP SUMMARY

Clinical Investigation Name and Number	CRD_1030 Gemini
Title	Study of Gemini Rechargeable Spinal Cord Stimulation (SCS) System
Objective(s)	The objective of this study is to collect confirmatory data to show that the Gemini Spinal Cord Stimulation neuromodulation system functions as intended in a clinical setting.
Device Under Investigation	Gemini rechargeable Spinal Cord Stimulation (SCS) System
Number of Subjects Required for Inclusion in Clinical Investigation	The study is designed to report on 20 subjects who receive a Gemini SCS implant and complete follow-up. [REDACTED]
Clinical Investigation Design	Prospective, pre-market, non-randomized, multi-center, single-arm study
Confirmatory Safety Endpoint	The rate of serious adverse events adjudicated as related to the IPG and/or charging system.
Subject Follow-up	
 • Enrollment/Baseline • Permanent Implant • 2-week (10-14 days) follow-up post implant (in office, phone call, telemedicine) • 6-week (30-45 days) follow-up post implant (in office)
Inclusion Criteria	
 1. Subject is indicated for an SCS system, or has an implanted SCS system and is scheduled to receive an IPG replacement. 2. Subject is scheduled to receive a new IPG permanent implant and has completed a successful SCS trial in the last 6-months, OR subject is scheduled to undergo an all-in-one procedure OR has an implanted SCS system for an approved chronic pain indication. 3. Subject has a documented NRS pain score of ≥ 6 after at least 5 days without stimulation OR has an implanted functioning SCS system with NRS pain score of ≤ 4. 4. Subject must provide written informed consent prior to any clinical investigation-related procedure. 5. Subject is at least 18 years at the time of enrollment. 6. Subject is capable and willing to recharge an implanted IPG.

Clinical Investigation Plan

Exclusion Criteria	
1. Subject's SCS trial was unsuccessful.2. Subject is currently participating, or intends to participate, in another clinical investigation that may confound the results of this study, as determined by Abbott.3. Subject has or will receive more than one IPG.4. Subject is pregnant or breastfeeding or plans to become pregnant during the clinical investigation follow-up period.5. Subject has other anatomic or comorbid conditions, or other medical, social, or psychological conditions that, in the investigator's assessment, could limit the subject's ability to participate in the clinical investigation.6. Subject has or is scheduled to receive an intrathecal pump.7. Subject is part of a vulnerable population (section 5.2.2 of the clinical investigational plan).
---------------------------	---

1.0 SYNOPSIS OF STUDY DESIGN

1.1 Purpose of the Statistical Analysis Plan

This statistical analysis plan (SAP) is to provide a detailed and comprehensive description of the planned methodology and analysis to be used for Clinical Investigation Plan (CIP) 10407, the GEMINI study (CRD_1030). This plan is based on CIP Version A, April 2021.

1.2 Clinical Investigation Objectives

The objective of this study is to collect confirmatory data to show that the Gemini SCS neuromodulation system functions as intended in a clinical setting.

1.3 Clinical Investigation Design

This is a pre-market, prospective, single-arm, non-randomized, open-label multi-center clinical study designed to show that the Gemini SCS neurostimulation system functions as intended in a clinical setting.

The study is designed to report on 20 subjects who receive a Gemini SCS implant and complete follow-up. [REDACTED]

1.4 Endpoints

1.4.1 Confirmatory Safety Endpoint

The confirmatory safety endpoint is the rate of serious adverse events adjudicated as related to the investigational IPG and/or charging system. No formal hypothesis test will be evaluated, but data for the endpoint will be used to confirm whether Gemini SCS system functions as intended.

1.4.2 Additional Endpoints

Additional endpoints are reported using descriptive statistics, without hypothesis testing:

- Serious adverse events other than confirmatory endpoint with their relatedness (such as device, procedure, stimulation, charging, COVID, or MRI)
- Non-serious adverse events related to device, procedure, stimulation, charging, COVID, or MRI (investigational device and on-market devices)

Additional data collected:

- Patient satisfaction
- Patient experience with charging
- NRS for pain intensity
- PROMIS-29
- Charging history
- Stimulation programs used
- Stimulation programs available

Statistical Analysis Plan

2.0 ANALYSIS CONSIDERATIONS

2.1 Analysis Populations

A subject is considered enrolled in the study when the following conditions are met:

1. Subject has provided written informed consent, and
2. Subject has been determined to meet all inclusion and do not meet any exclusion criteria.

The following populations will be used in the analysis for this study.

[REDACTED]

2.2 Statistical Methods

2.2.1 Descriptive Statistics for Continuous Variables

For continuous variables (e.g., age), results will be summarized as number of observations, means, and standard deviations, and where applicable, with quartiles, minimums, maximums, and 95% confidence intervals for the means. Difference between baseline and 6-week follow-up, when specified, will be summarized with the means of the difference, and the 95% confidence interval of the differences.

2.2.2 Descriptive Statistics for Categorical Variables

For categorical variables (e.g. gender), results will be summarized with subject counts and percentages/rates, and where applicable, with exact 95% Clopper-Pearson¹ confidence intervals.

2.3 Endpoint Analysis

2.3.1 Confirmatory Safety Endpoints

The confirmatory safety endpoint for this study is the rate of Serious Adverse Events (SAEs) related to the IPG and/or charging system.

No formal hypothesis is formulated for this study. The confirmatory endpoint will be summarized as the number and percentage of subjects with IPG and/or charging system related SAEs, along with exact 95% Clopper-Pearson confidence intervals.

The confirmatory endpoint will be analyzed using safety population defined in 2.1. The evaluable subjects will include those who complete their 6-week visit or had IPG and/or charging related SAE at/prior to their termination before 6 weeks visit.

Charging system related SAE(s) will also be analyzed separately using safety population defined in 2.1. The evaluable subjects will include those who complete their 6-week visit or had charging system related SAE at/prior to their termination before 6 weeks visit.

Statistical Analysis Plan

2.4 Sample size Calculation

[REDACTED]

2.5 Interim Analysis

[REDACTED]

2.6 Timing of Analysis

The analysis will be performed after all enrolled subjects have completed their 6-week visits or withdrawn from study.

2.7 Handling of Missing Data

Confirmatory endpoint analysis will be based on available data. No imputation for missing data will be performed.

3.0 DESCRIPTIVE ENDPOINTS AND ADDITIONAL DATA

3.1 Baseline and Demographic Characteristics.

Baseline and demographic variables will be summarized using the methods defined in 2.2 based on the safety population defined in 2.1. Adverse Events (AE)

3.2 Safety population defined in 2.1 will be included in this analysis. Serious adverse events (SAEs) and AEs, will be summarized using number of events, the percentage of subjects with events and by the relatedness (such as related to device, procedure, stimulation, charging, COVID, or MRI) of events. Subject Early Termination

Subject early termination reasons including deaths, withdrawals, lost-to-follow-up, etc. will be summarized for all enrolled subjects.

3.3 Protocol Deviation

Protocol deviations will be summarized by category for subjects in whom a protocol deviation was reported. Number of protocol deviations and number of subjects with deviation will be summarized by deviation category.

Statistical Analysis Plan

3.4 Descriptive Performance Endpoints or Additional Data

Descriptive Endpoints

The descriptive endpoints will be analyzed using the methods defined in 2.2 based on implanted population defined in 2.1. The descriptive endpoints will be analyzed at baseline and at 6 weeks if applicable.

Descriptive endpoints include:

- Patient satisfaction
- Patient experience with charging
- NRS score change
- PROMIS-29 change
- Charging history

The following charging history will be summarized using the methods defined in 2.2

- Time between implant and first charging session in days
- Number of charging sessions
- The rate of charging sessions per follow-up week
The numerator will be the total number of charging sessions. The denominator will be the total follow-up duration (in weeks) from the date of first charging started to the last follow-up date
- Average duration of charging (in hours) per charging session
- Average charging interruptions per charging session
- Rate of charging sessions with Overheat protection events, which is defined as total number of sessions with overheating protection flag/total number of charging sessions
- The average percent of battery at end of the charging sessions per charging session

- Stimulation programs used
- Stimulation programs available

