5.3.2. Inclusion Criteria

1. Subject is indicated for an SCS system, or has an implanted SCS system and is scheduled to receive an IPG replacement.
2. Subject is scheduled to receive a new IPG permanent implant and has completed a successful SCS trial in the last 6-months, OR subject is scheduled to undergo an all-in-one procedure OR has an implanted SCS system for an approved chronic pain indication.
3. Subject has a documented NRS pain score of ≥ 6 after at least 5 days without stimulation OR has an implanted functioning SCS system with NRS pain score of ≤ 4 .
4. Subject must provide written informed consent prior to any clinical investigation-related procedure.
5. Subject is at least 18 years at the time of enrollment.
6. Subject is capable and willing to recharge an implanted IPG.

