6. TREATMENT AND EVALUATION OF ENDPOINTS

6.1. Baseline/Pre-procedure

6.1.1. Baseline Assessments

Baseline visit should occur no more than 15 days after enrollment. If an SCS trial was performed, baseline pain and functional assessments should be made after at least 5 days without stimulation. If it is not possible to have stimulation off for at least 5 days, baseline data may be obtained from medical records from the last 6 months. The baseline pain score reported should be the score used to evaluate the inclusion and exclusion criteria (no stimulation NRS \geq 6, stimulation NRS \leq 4). The following baseline data will be collected:

- Patient demographics
- Pain diagnosis (specifically the subject's primary indication for neuromodulation) and pain location
- Pain history (time with chronic pain, previous treatment)
- Prior interventions (e.g. physical therapy, injections, surgeries) to treat the presenting condition
- Numeric Rating Scale (NRS) for pain intensity
- PROMIS-29
- Adverse events (if applicable)

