6.2. Permanent System Implant

Implantation of the neurostimulation system will be performed according to the sites standard operating procedures and should be consistent with instructions in the IFU. It should be performed after the baseline assessments and no later than 60 days from the enrollment visit. If it has not occurred within 60 days after Enrollment, the subject will be withdrawn (Section 5.5). Following system implantation, the stimulator will be activated and programmed by trained personnel either during post-operative recovery or at an office visit in accordance with the physician's and hospital's standard operating procedures. The subject's spinal cord stimulator will be programmed according to the most recent Abbott programming guidance. After programming, the subject will receive a patient programmer and will be instructed on how to use the system to relieve their pain.

The investigator or delegate will instruct the subject on use of the charger, including weekly charging after the initial wound healing period.

Clinical Investigation Plan

A charging plan for the patient should satisfy the following criteria:

- First battery charge prior to attending the 2-week follow up visit
- Weekly battery charge after 2 weeks

The following information will be collected at the permanent system implant:

- Neurostimulation system device information
- Lead type(s) and location
- Programming parameters subject is using at the end of device activation
- All serious adverse events including deaths (if applicable)
- Non-serious adverse events related to device, procedure, stimulation, charging, or MRI (if applicable)
- Withdrawal (if applicable)
- Device deficiency (if applicable)
- Additional Surgery (if applicable)

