3.4.1 Additional Analyses

Battery consumption per day will be summarized using the method defined in 2.2.1.

The battery consumption per day is calculated as

$$\frac{\sum(\text{Battery (\%)} \text{ usage between two consecutive charging sessions})}{\sum(\text{days between the two consecutive charging sessions})}$$

For example, the first charging is on Mar 27th, 2021, the battery (%) is 85% at the end of the charging session. The next charging is April 10th, 2021 and the battery is 29% at beginning of charging. The battery usage is calculated as 85%-29%=56%. There are 14 days between the two charging sessions.

Other additional analysis may be needed for exploratory purposes.

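### SAP 3.4 plans one pooled NRS change for two entry routes with different baselines and stimulation states, so the mean can depend on the route mix (additional descriptive data only)

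*SAP*

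**What the plan says.** **Entry.** Protocol 5.3.2, criterion 3, has two branches. The first reads "Subject has a documented NRS pain score of ≥ 6 after at least 5 days without stimulation". The second reads "OR has an implanted functioning SCS system with NRS pain score of ≤ 4".

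**Baseline.** Protocol 6.1.1 carries the branches into the baseline value: "The baseline pain score reported should be the score used to evaluate the inclusion and exclusion criteria". It labels the two cut-offs by stimulation state, the higher one without stimulation and the lower one with it.

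**Follow-up.** Protocol 6.2 says: "Following system implantation, the stimulator will be activated and programmed by trained personnel". Protocol 6.3.3.1 has subjects rate their pain at the study visit on a 0 to 10 scale, higher being worse.

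**Analysis.** SAP 3.4 lists NRS score change among the descriptive endpoints and says: "The descriptive endpoints will be analyzed using the methods defined in 2.2 based on implanted population defined in 2.1". It adds: "The descriptive endpoints will be analyzed at baseline and at 6 weeks if applicable". SAP 2.2.1 supplies the method: "Difference between baseline and 6-week follow-up, when specified, will be summarized with the means of the difference", together with a 95% confidence interval. SAP 3.4.1 leaves a general opening: "Other additional analysis may be needed for exploratory purposes".

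**Status.** Protocol 4.2 and SAP 1.4.2 place NRS under additional data collected. No test or threshold is attached to it in the visible text.

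**The concern.** NRS change does not mean the same thing in the two branches. A subject who enters with a score of 6 or more goes from no stimulation to stimulation with Gemini. A subject who enters with a score of 4 or less goes from a functioning earlier system to Gemini. The first contrast resembles a treatment effect. The second asks whether relief is kept after the change of system.

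A single mean over both describes neither. It can move with recruitment alone, and a rise in pain in the lower-score route can be covered by the fall in the higher-score route. What is at stake is how one descriptive result is read.

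**Working it through.** The documents give no expected NRS change, SD or route mix, so there is no planned figure to reproduce. Call the branch with NRS of at least 6 route A and the branch with NRS of at most 4 route B.

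**1. What follows from the documents**

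Inputs: the cut-offs 6 and 4 (Protocol 5.3.2), the 0 to 10 scale (Protocol 6.3.3.1) and n = 20 (SAP 1.3). The recorded baseline is taken to be the eligibility score, as Protocol 6.1.1 asks.

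- Possible individual change, route A: from 0 − 10 = −10 to 10 − 6 = +4.
- Possible individual change, route B: from 0 − 4 = −4 to 10 − 0 = +10.
- Let Ba and Bb be the route baseline means and x a 6-week mean common to both routes. The mean changes are x − Ba and x − Bb, and they differ by Ba − Bb. With Ba between 6 and 10 and Bb between 0 and 4, this gap is at least 6 − 4 = 2 and at most 10 − 0 = 10 points.
- At fixed route means, one subject in route B instead of A moves the pooled mean by gap/20, at least 2/20 = 0.1 point.
- Fifteen rather than 5 subjects in route B move it by gap × 10/20, at least 1.0 point.

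The 2-point minimum needs equal 6-week means. If the mean change itself were equal in both routes, the pooled mean would not depend on the mix.

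**2. Illustration of the mix (assumed values)**

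Assume mean changes of −4 (A) and 0 (B) and a within-route SD of s = 2. Then, with ca and cb the route mean changes:

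- m = (na·ca + nb·cb)/20
- SD² = [(na − 1)s² + (nb − 1)s² + na(ca − m)² + nb(cb − m)²]/19
- 95% CI = m ± t(19)·SD/√20, with t(19) = 2.093

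| In route B | Pooled mean | SD | 95% CI |
|---|---|---|---|
| 5 of 20 | −3.0 | 2.64 | −4.2 to −1.8 |
| 10 of 20 | −2.0 | 2.83 | −3.3 to −0.7 |
| 15 of 20 | −1.0 | 2.64 | −2.2 to +0.2 |

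Nothing within either route differs between these rows.

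**3. Illustration of offsetting (assumed values)**

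Assume mean changes of −4 (A, 15 subjects) and +2 (B, 5 subjects), s = 2.

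- m = (15 × −4 + 5 × 2)/20 = −2.5
- SD² = [14 × 4 + 4 × 4 + 15 × 1.5² + 5 × 4.5²]/19 = 207/19 = 10.89, so SD = 3.30
- CI = −2.5 ± 2.093 × 3.30/√20 = −2.5 ± 1.54, or −4.0 to −1.0
- With s = 1.5 the CI is −3.9 to −1.1, and with s = 2.5 it is −4.2 to −0.8.
- With +1 instead of +2 in route B (s = 2), the pooled mean is −2.75 (CI −4.1 to −1.4).

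By route (s = 2, half-width t(n − 1)·s/√n), the result is −4.0 (CI −5.1 to −2.9) in A and +2.0 (CI −0.5 to +4.5) in B. The split shows the direction in B, but with 5 subjects it does not establish a worsening.

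**The case against.** The strongest reply is that no defect is proven. The population definitions, the sample size sections, SAP 4.0 and the protocol revision history are redacted, and a split or quota could sit there. SAP 1.1 also says that the SAP rests on CIP Version A, so criterion 3 may have changed after it was written. Both points stand. They confine the finding to the visible text, and a reader who concludes that the SAP contains no split goes further than the documents allow.

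Second, nothing visible turns on NRS change. Protocol 4.1 and SAP 1.4.1 tie the judgement that the system works as intended to the safety endpoint. That also stands, and it fixes the severity. A reader might infer that the confirmatory conclusion is compromised, but the documents give no support for that.

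Third, SAP 3.4 also reports levels at baseline and 6 weeks, and SAP 2.2.1 adds the SD and, where applicable, quartiles and range. With clusters at 6 to 10 and 0 to 4, a reader may well notice the mixture. These summaries still do not give the change within each route. The allowance in SAP 3.4.1 names no split.

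Fourth, a reader might infer that the pooled mean must depend on the mix, or that the baseline score always reveals the route. Neither is assured. Equal mean changes would remove the dependence. Protocol 6.1.1 says only what the baseline score should be and in some cases allows baseline data from medical records, while Protocol 6.3.3.1 defines the NRS as pain at the visit. A score recorded on the visit day could fall outside both ranges, and then the 2-point minimum is not guaranteed either.

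**Conclusion.** The point holds for the visible text as a cheap improvement (severity: could be changed). As written, SAP 3.4 with SAP 2.2.1 gives a mean NRS change that mixes two different contrasts and can depend on the route mix.

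The size that needs no outside figure is conditional. If the 6-week means are equal and the recorded baselines are the eligibility scores, the route mean changes differ by at least 2 points, and 15 rather than 5 of 20 subjects in the lower-score route shifts the pooled mean by at least 1.0 point. The pooled −2.5 (CI −4.0 to −1.0) alongside a rise of 2 points in one route is an illustration only; its route changes, SD and mix are all assumed. If few or no subjects enter by the lower-score route, the effect shrinks or vanishes.

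**What to change.** In SAP 3.4, report NRS at baseline, at 6 weeks and as change by the criterion-3 branch documented at eligibility.

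- Use the baseline score only as a cross-check on the branch. Do not substitute new implant versus replacement: a subject with an existing system could enter by the off-stimulation branch.
- Add an individual-subject listing, because the groups will be small.
- Give n and mean for each route, and SD and 95% CI only where the group size allows. With one subject neither can be computed.
- Show any pooled mean change only beside the route results.
- PROMIS-29 change may follow the same split. A different stimulation state at its baseline is an inference, however, since Protocol 6.1.1 does not state one for PROMIS-29 in subjects with a functioning implant.

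Before editing, the sponsor should check whether the redacted text already has a split and whether criterion 3 changed after CIP Version A.

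The cost is SAP wording and a table row or listing. The branch should be available from the eligibility documentation, but the case report forms are kept separately, so whether it is captured as a data item needs confirming. The statistical downside is width: with an assumed SD of 2, the within-route half-width is about 2.5 points at n=5 and 1.4 at n=10 (1.9 to 3.1 and 1.1 to 1.8 for SDs of 1.5 to 2.5). The split serves description, not inference.

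### On the visible text, NRS and PROMIS-29 change are averaged over off-stimulation and on-stimulation baselines; SAP 3.4 should report change by baseline stimulation state (minor)

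*SAP*

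**What the plan says.** **Entry.** Protocol 5.3.2 admits new implants after a successful trial, all-in-one procedures, and replacements: criterion 2 ends "OR has an implanted SCS system for an approved chronic pain indication". Criterion 3 requires either a documented NRS of at least 6 after 5 or more days without stimulation, or that the subject "has an implanted functioning SCS system with NRS pain score of" 4 or less.

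**Baseline.** Protocol 6.1.1 carries this split into the data: "The baseline pain score reported should be the score used to evaluate the inclusion and exclusion criteria". It then restates both limits, one for each stimulation state. For subjects who had a trial, "If an SCS trial was performed, baseline pain and functional assessments should be made after at least 5 days without stimulation". If stimulation cannot be off that long, chart data from the preceding 6 months may be used. PROMIS-29 is collected at the same baseline.

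**Analysis.** SAP 3.4 lists NRS change and PROMIS-29 change among the descriptive endpoints. It says: "The descriptive endpoints will be analyzed using the methods defined in 2.2 based on implanted population defined in 2.1", and adds: "The descriptive endpoints will be analyzed at baseline and at 6 weeks if applicable". SAP 2.2.1 says that a baseline to 6-week difference, when specified, "will be summarized with the means of the difference, and the 95% confidence interval of the differences". For continuous variables it also gives SDs and, where applicable, quartiles and range. No visible text names a stratum. SAP 3.4.1 leaves room for more, without commitment: "Other additional analysis may be needed for exploratory purposes".

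**The concern.** Change from baseline answers a different question in each group. For a subject with an off-stimulation baseline, it measures the start of SCS therapy. For a subject who arrives on a working system, it measures whether relief is maintained after the switch to Gemini.

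Protocol 15.1 expects pain improvement comparable to that with other marketed SCS systems. If that holds, the first group should show a large fall in NRS and the second should stay near zero. An on-stimulation subject who enters at 2 and remains at 2 has done well, yet pulls the pooled mean towards no effect.

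A single mean then describes neither group, and it can move with the mix of entry routes even if every site follows the plan and the device performs identically. What is at stake is how these descriptive performance data are read in a study meant to show that the system functions as intended.

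**Working it through.** The documents show no effect size, SD, entry mix or sample-size figure for these endpoints, so there is no stated figure to reproduce.

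**Inputs**
- NRS scale 0 to 10, higher is worse (Protocol 6.3.3.1).
- Baseline NRS of 6 to 10 off stimulation, 0 to 4 on stimulation (Protocol 5.3.2 and 6.1.1).
- N = 20 subjects to be reported (Protocol 5.6; SAP 1.3).
- k = number with an on-stimulation baseline. It is not visible, so it is varied.
- Assumptions, marked where used: equal 6-week scores in both groups; within-group SD of change.

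**1. Largest possible improvement.** It equals the baseline score: 6 to 10 points off stimulation, and 4 points at most on stimulation. The highest attainable pooled mean improvement is (4k + 10(20 − k))/20 = 10 − 0.3k:
- k = 5: 8.5
- k = 10: 7.0
- k = 15: 5.5

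This uses only the scale and the entry limits. It is an arithmetic ceiling, not an expected result.

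**2. Shift caused by entry mix.** The smallest gap between the two baselines is 6 − 4 = 2. If 6-week scores are equal (assumption), the group mean changes differ by at least 2. Each subject moved between states then shifts the pooled mean by at least 2/20 = 0.1. Relative to all-off entry the shift is at least 2k/20:
- k = 2: 0.2
- k = 5: 0.5
- k = 10: 1.0
- k = 15: 1.5

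**3. Illustration with assumed values.** Take baselines of 7.5 (off) and 3 (on), a 6-week score of 3 in both groups, and a within-group SD of 1.5. The off group changes by 3 − 7.5 = −4.5 and the on group by 3 − 3 = 0. Pooled change = [(20 − k)(−4.5) + k(0)]/20:
- k = 0: −4.50
- k = 5: −3.375 (95% CI −4.54 to −2.21)
- k = 10: −2.25 (−3.54 to −0.96)
- k = 15: −1.125 (−2.29 to 0.04)
- k = 20: 0.00

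Device performance is the same in every row. With the closest permitted baselines (6 and 4) and a 6-week score of 3, the pooled change still runs from −3.00 at k = 0 to −1.00 at k = 20.

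**4. Precision, with an assumed within-group SD of 2.** For fixed k and a gap d between group mean changes, pooled SD = √(4 + [k(20 − k)/20]d²/19), and the half-width is 2.093 × SD/√20.
- d = 0: 0.94
- d = 2: 0.98 (k = 2), 1.02 (k = 5), 1.05 (k = 10)
- d = 6: 1.27 (k = 2), 1.56 (k = 5), 1.72 (k = 10)

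Separate groups: n = 10 gives 2.262 × 2/√10 = 1.43; n = 5 gives 2.776 × 2/√5 = 2.48.

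The PROMIS-29 effect cannot be estimated from the documents.

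**The case against.** **No decision depends on these numbers.** Protocol 4.2 lists both changes as additional data, with no hypothesis test, and the visible text gives no success threshold or comparator. Protocol 1.1.2 says that the study focuses on safety events that could be attributed to the new charging system. This stands, and it limits the severity. It does not answer the point, because description is what the pooling weakens.

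**The planned outputs already help.** Baseline and 6-week summaries, with quartiles and range where applicable, would reveal a mixed sample, since permitted baselines are only at or below 4 or at or above 6. That is correct, but separate summaries at each visit cannot recover the change within each state. SAP 3.4.1 permits a split without promising one.

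**Redacted text may contain the rule.** The population definitions, including the implanted population, and all of SAP 4.0 are hidden. A reader might infer that the sponsor has no subgroup rule. The documents do not support that; only the visible text can be judged.

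**The size rests on assumptions.** Neither the entry mix nor the 6-week scores are given, and if k is near 0 or 20 the effect nearly vanishes. This stands, which is why the shifts are shown as a range and as minimum values under the equal-score assumption.

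**Splitting costs precision.** At a 2-point gap, pooling widens the half-width only from 0.94 to 1.05 at most, while separate groups of 10 give 1.43. A reader might infer that pooling makes the estimate too imprecise. At that gap the figures do not show this. The case rests on interpretation.

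**PROMIS-29.** A reader might infer that its baseline stimulation state is uncontrolled throughout. It is not: for subjects who had a trial, Protocol 6.1.1 covers functional as well as pain assessments. The state is left open for subjects entering on a functioning system, and is not spelled out for chart-derived baselines.

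**Conclusion.** The point holds on the visible text, as a minor one. The plan defines two non-overlapping baseline states and then summarises change over both as one mean with a 95% CI. That mean depends on entry mix as well as on device performance. Under the equal-score assumption, the mix alone accounts for at least 0.1 NRS point per subject out of 20, and next to nothing if one route dominates.

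A reader might go further and infer that the study's conclusion or its safety result is compromised. The documents do not support that. The confirmatory endpoint is the rate of serious adverse events related to the IPG or charging system, and it does not use these scores. Nor can one say that the pooled figure will in fact mislead, because the entry mix is not visible. Confidence is medium, mainly because of the redactions.

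**What to change.** In SAP 3.4, report NRS change separately by baseline stimulation state, and PROMIS-29 change by the same qualifying state. Keep any pooled line as secondary. If a group has fewer than about 5 subjects, list individual values instead of a CI. Split by stimulation state, not by new versus replacement implant, because a replacement subject can also qualify with an off-stimulation score. If redacted text already contains this split, the sponsor need only confirm it.

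For NRS the state follows from the qualifying score, so no new data are needed. The cost is one table split and wider descriptive intervals: with an assumed SD of 2, half-widths of 1.43 at n = 10 and 2.48 at n = 5, against 0.94 for a pooled 20 with no gap.

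Optional clarifications: Protocol 6.1.1 could say that PROMIS-29 is taken in the same stimulation state as the qualifying NRS, including when chart data are used, and that this state is recorded if the CRF does not already do so. That is a sentence or two and at most one CRF item. The 5-day off-stimulation requirement needs no restating, since criterion 3 already imposes it.
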